### Geriatric Use

Clinical studies of propranolol did not include sufficient numbers of subjects aged 65 and over to determine whether they respond differently from younger subjects. Other reported clinical experience has not identified differences in responses between the elderly and younger patients. In general, dose selection for an elderly patient should be cautious, usually starting at the low end of the dosing range, reflecting the greater frequency of decreased hepatic, renal, or cardiac function, and of concomitant disease or other drug therapy.

### Adverse Reactions

The following adverse events were observed and have been reported in patients using propranolol.

Cardiovascular: Bradycardia; congestive heart failure; intensification of AV block; hypotension; paresthesia of hands; thrombocytopenic purpura; arterial insufficiency, usually of the Raynaud type.

Central Nervous System: Light-headedness, mental depression manifested by insomnia, lassitude, weakness, fatigue; catatonia; visual disturbances; hallucinations; vivid dreams; an acute reversible syndrome characterized by disorientation for time and place, short-term memory

loss, emotional lability, slightly clouded sensorium, and decreased performance on neuropsychometrics. For immediate-release formulations, fatigue, lethargy, and vivid dreams appear dose-related.

Gastrointestinal: Nausea, vomiting, epigastric distress, abdominal cramping, diarrhea, constipation, mesenteric arterial thrombosis, ischemic colitis.

Allergic: Hypersensitivity reactions, including anaphylactic/anaphylactoid reactions, pharyngitis and agranulocytosis; erythematous rash, fever combined with aching and sore throat; laryngospasm, and respiratory distress.

Respiratory: Bronchospasm.

Hematologic: Agranulocytosis, nonthrombocytopenic purpura, thrombocytopenic purpura.

Autoimmune Systemic Autoimmune: Systemic lupus erythematosus (SLE).

Skin and mucous membranes: Stevens - Johnson syndrome, toxic epidermal necrolysis, dry eyes, exfoliative dermatitis, erythema multiforme, urticaria, alopecia, SLE-like reactions, and psoriasisiform rashes. Oculomucocutaneous syndromes involving the skin, serous membranes and conjunctivae reported for a beta blocker (practolol) have not been associated with propranolol.

Genitourinary: Male impotence; Peyronie's disease.

### **Overdosage**

Propranolol is not significantly dialyzable. In the event of over dosage or exaggerated response, the following measures should be employed:

General: If ingestion is or may have been recent, evacuate gastric contents, taking care to prevent pulmonary aspiration.

Supportive Therapy: Hypotension and bradycardia have been reported following propranolol overdose and should be treated appropriately. Glucagon can exert potent inotropic and

## A Pilot “Window of Opportunity” Neoadjuvant Study of Propranolol in Breast Cancer

Principal Investigator: [name]

Co-Principal Investigator: [name], MBA

chronotropic effects and may be particularly useful for the treatment of hypotension or depressed myocardial function after a propranolol overdose. Glucagon should be administered as 50-150 mcg/kg intravenously followed by continuous drip of 1-5 mg/hour for positive chronotropic effect. Isoproterenol, dopamine or phosphodiesterase inhibitors may also be useful. Epinephrine, however, may provoke uncontrolled hypertension. Bradycardia can be treated with atropine or isoproterenol. Serious bradycardia may require temporary cardiac pacing.

The electrocardiogram, pulse, blood pressure, neurobehavioral status and intake and output balance must be monitored. Isoproterenol and aminophylline may be used for bronchospasm.

### Dosage and Administration

#### General

Because of the variable bioavailability of propranolol, the dose should be individualized based on response.

#### Hypertension

The usual initial dosage is 40 mg Propranolol twice daily, whether used alone or added to a diuretic. Dosage may be increased gradually until adequate blood pressure control is achieved. The usual maintenance dosage is 120 mg to 240 mg per day. In some instances a dosage of 640 mg a day may be required. The time needed for full antihypertensive response to a given dosage is variable and may range from a few days to several weeks. While twice-daily dosing is effective and can maintain a reduction in blood pressure throughout the day, some patients, especially when lower doses are used, may experience a modest rise in blood pressure toward the end of the 12-hour dosing interval. This can be evaluated by measuring blood pressure near the end of the dosing interval to determine whether satisfactory control is being maintained throughout the day. If control is not adequate, a larger dose, or 3-times-daily therapy may achieve better control.

#### Angina Pectoris

## A Pilot “Window of Opportunity” Neoadjuvant Study of Propranolol in Breast Cancer

Principal Investigator: [name]

Co-Principal Investigator: [name], MBA

Total daily doses of 80 mg to 320 mg Propranolol, when administered orally, twice a day, three times a day, or four times a day, have been shown to increase exercise tolerance and to reduce ischemic changes in the ECG. If treatment is to be discontinued, reduce dosage gradually over a period of several weeks.

### Atrial Fibrillation

The recommended dose is 10 mg to 30 mg Propranolol three or four times daily before meals and at bedtime.

### Myocardial Infarction

In the Beta-Blocker Heart Attack Trial (BHAT), the initial dose was 40 mg t.i.d., with titration after 1 month to 60 mg to 80 mg t.i.d. as tolerated. The recommended daily dosage is 180 mg to 240 mg Propranolol per day in divided doses. Although a t.i.d. regimen was used in the BHAT and a q.i.d. regimen in the Norwegian Multicenter Trial, there is a reasonable basis for the use of either a t.i.d. or b.i.d. regimen. The effectiveness and safety of daily dosages greater than 240 mg for prevention of cardiac mortality have not been established. However, higher dosages may be needed to effectively treat coexisting diseases such as angina or hypertension (see above).

### Migraine

The initial dose is 80 mg Propranolol daily in divided doses. The usual effective dose range is 160 mg to 240 mg per day. The dosage may be increased gradually to achieve optimum migraine prophylaxis. If a satisfactory response is not obtained within four to six weeks after reaching the maximum dose, Inderal therapy should be discontinued. It may be advisable to withdraw the drug gradually over a period of several weeks.

### Essential Tremor

The initial dosage is 40 mg Propranolol twice daily. Optimum reduction of essential tremor is usually achieved with a dose of 120 mg per day. Occasionally, it may be necessary to administer 240 mg to 320 mg per day.

**A Pilot “Window of Opportunity” Neoadjuvant Study of Propranolol in Breast Cancer**

**Principal Investigator: [name]**

**Co-Principal Investigator: [name], MBA**

**Hypertrophic Subaortic Stenosis**

The usual dosage is 20 mg to 40 mg Propranolol three or four times daily before meals and at bedtime.

**Pheochromocytoma**

The usual dosage is 60 mg Propranolol daily in divided doses for three days prior to surgery as adjunctive therapy to alpha-adrenergic blockade. For the management of inoperable tumors, the usual dosage is 30 mg daily in divided doses as adjunctive therapy to alpha-adrenergic blockade.

**How Supplied**

Dispense in a well-closed, light-resistant container as defined in the USP. Protect from light. Use carton to protect contents from light. Store at controlled room temperature 20° to 25° C (68° to 77° F); excursions permitted to 15° to 30° C (59° to 86° F). Dispense in a well-closed, light-resistant container as defined in the USP. Protect from light.

**Toxicity and Adverse Events**

Known side effects of propranolol include hypoglycemia, hypotension, bradycardia, and bronchospasm. It was recently reported in a study of over 460 patients with infantile hemangioma that a dose of propranolol up to 3 mg/kg/day for up to 6 months resulted in no significant difference in adverse events between the placebo and treatment group [9]. Safety assessments will be performed at in-clinic visits by analysis of adverse events (i.e. any change in condition between the time of informed consent and the end of the trial); laboratory investigations (including measurement of glucose levels from finger-prick blood samples), physical examination (including pulmonary auscultation, liver palpation, assessment of vital signs, and assessment of cognitive function), and electrocardiography.

**8. Toxicity Monitoring and Dose Modification**

Patients will be closely monitored during the entirety of this study for known important risks associated with propranolol therapy. A baseline EKG will be done and read by the cardiologist

**A Pilot “Window of Opportunity” Neoadjuvant Study of Propranolol in Breast Cancer**  
**Principal Investigator: [name]**  
**Co-Principal Investigator: [name], MBA**

who will determine any abnormality that would preclude participation. Patients with a normal EKG will be allowed to participate on this trial. After taking the initial dose of propranolol, the study staff will contact the study participant via phone within 4-6 hours in order to follow-up and determine if the patient is having any side effects from the medication. If the patient is found to have side effects, the study staff that conducts the call will immediately notify the PI and/or co-investigators. They will then determine if the study treatment should continue or if the patient should stop treatment. Patients will also be asked to call the study coordinator at any time during the study if they have any further side effects.

In addition to in-clinic assessments, blood pressure and pulse monitoring will be performed and recorded by the participants in-home on a daily basis, twice daily, using supplied monitors to ensure that propranolol is not adversely affecting their blood pressure levels or pulse below established threshold levels. If the blood pressure of any participant drops below 100/60 and/or pulse is <55, propranolol will be stopped and the patient taken off protocol. The event will be counted as an adverse event.

A board certified cardiologist ([name]) who is on active staff at UMC and Texas Tech University Health Sciences Center will review the history and physical exam data, and the EKG to assure that the patient is unlikely to have pre-existing cardiac disease. The cardiologist will also be available throughout the study in order to see patients as needed if the PI and sub-investigators determine it would be beneficial to the patient.

All toxicities will be graded according to CTCAE 4.0. The dose of Propranolol will not be modified. If a patient is found to have an AE grade of 2 or more, treatment will stop and the patient will complete the end of treatment visit.

Study treatment will continue 25 days until there is an unacceptable toxicity, the subject is non-compliant with trial procedures or if the principal investigator and co-investigators feel that it is unsafe for the patient to continue with the treatment.

## A Pilot “Window of Opportunity” Neoadjuvant Study of Propranolol in Breast Cancer

Principal Investigator: [name]

Co-Principal Investigator: [name], MBA

### **9. Statistical Consideration and Data Analysis:**

The primary endpoint of this study is the change in tumor proliferative index following propranolol treatment. We expect to have a moderate effect size in the tumor proliferative index following propranolol treatment. We anticipate having at least 10% mean change in the tumor proliferative index following propranolol treatment with a common standard deviation of 15% (a conservative estimate). Using this information, a total sample size of 25 patients achieves more than 85% power with 5% level of significance using a two tailed paired t-test. After adding an estimated 20% dropout rate, we propose to recruit a total of 30 patients in the study. This sample size is sufficient to determine the high correlation (80% or more) between change in proliferation marker and expression of beta adrenergic receptors with a confidence width equal to 30%. The sample size was determined using PASS software ([www.ness.com](http://www.ness.com)).

*Expected results:* Given the promising results of the recent retrospective clinical trials demonstrating that propranolol significantly reduces breast cancer metastasis and improves cancer patient survival, as well as the promising case studies showing rapid and complete remission of highly aggressive tumors following propranolol administration, we are highly optimistic that we will see a statistically and clinically significant reduction in the proliferative index of breast cancer tumors following the treatment. If our findings are promising, the data acquired could lay the foundation for using beta blockade as a safe, low cost therapeutic that could be especially useful in settings where many cancer patients do not possess the financial means for expensive novel therapeutics.

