## A Pilot “Window of Opportunity” Neoadjuvant Study of Propranolol in Breast Cancer

Principal Investigator: [name]

Co-Principal Investigator: [name], MBA

cost effectively evaluate molecular endpoints that support the efficacy of propranolol against breast cancer, and can be used to obtain subsequent larger grant funding from outside agencies for further clinical studies. WOO pre-surgical studies will expedite the process of testing propranolol in cancer patients by improving the understanding of its biologic effect early in its development, validating markers that may predict subsets of patients who will benefit from this drug, and targeting select patients in subsequent clinical trials that are powered to detect changes in clinical outcome. The following are the specific Aims of the study:

**Specific Aim #1: Evaluate the effect of the beta blocker propranolol on reducing the tumor proliferative index using Ki-67.**

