**Specific Aim #2: Correlate ADRB expression and intra-tumoral catecholamine signaling to propranolol treatment efficacy.**

**Specific Aim #3: Assess the safety, toxicity and adherence to propranolol.**

**4. Research Design and Methods:** This trial will be designed as a Phase II study using the “window-of-opportunity” (WOO) design in which the treatment-free window between breast cancer diagnosis and surgical tumor resection is used to study the biological effects of the beta blocker propranolol (Figure The proliferative index of the tumor after treatment will serve as the study’s primary endpoint. We have strategically chosen the WOO design as it allows us to cost effectively evaluate molecular endpoints that support the efficacy of propranolol against breast cancer, and can be used to obtain subsequent larger grant funding from outside agencies for further clinical studies. WOO pre-surgical studies will expedite the process of testing propranolol in cancer patients by improving the understanding of its biologic effect early in its development, validating markers that may predict subsets of patients who will benefit from this drug, and targeting select patients in subsequent clinical trials that are powered to detect changes in clinical outcome.

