**Tissue Microarray (TMA)** From the original paraffin block of each tumor, so-called donor block (30 cases, post-treatment), a 3mm wide and 5mm deep punch biopsy, corresponding to the tumor site, will be cut. These punch biopsies will be re-embedded in a new paraffin block (recipient block) to create TMA (possibly all 30 cases in one block). An excel file will be created that identified all the 30 cases by only numbers. From this TMA, multiple 3-4 microns thick slides will be cut at the UMC histology lab for Immunohistochemistry and will be provided to [name]'s lab from the UMC Pathology ([name]). **The team will need at least 4 slides from post-surgery tumor.** With access to each patient sample before and after propranolol treatment, we will have the ability to perform further analysis to understand at the molecular level how beta blockade is affecting the tumors, if the tumors are responding to the treatment, and if the tumors are actively taking steps to develop resistance to the treatment. We will begin by examining the expression of ADRB receptors in each tumor. We will subsequently examine the expression of several downstream effectors of ADRB signaling (as a positive control to confirm that propranolol is indeed blocking ADRB signaling in the treated tumors) and potential mechanisms of resistance

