### ADRB Receptor Analysis:

The three ADRB receptors that we will be looking at are ADRB1, ADRB2 and ADRB3 (which are the three beta adrenergic receptors expressed in humans, and the target of propranolol). We will attempt to statistically correlate treatment efficacy to the expression of each ADRB receptor. Tumor samples from the initial biopsy and surgical resection will be deidentified and stained via IHC for these specific ADRB receptors in [name] laboratory. We will require 3 tumor sections per collected tumor sample to accomplish this experiment. For this analysis, we will require 15 tumor sections pre-propranolol treatment and 15 tumor sections post-propranolol treatment. Each section will need to be 5 microns in thickness, thus we will need approximately 100-150 microns of tissue from each tumor to complete the analysis.

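### Aim 2 does not tie the ADRB predictor to pre-treatment tissue, and it needs a baseline-adjusted estimate beside the correlation with Ki-67 change

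*Combined protocol and SAP*

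**What the plan says.** Specific Aim #2 is to "Correlate ADRB expression and intra-tumoral catecholamine signaling to propranolol treatment efficacy". Two places describe the analysis.

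- Section 4, ADRB Receptor Analysis: "We will attempt to statistically correlate treatment efficacy to the expression of each ADRB receptor". The receptors are ADRB1, ADRB2 and ADRB3.
- Section 9: the sample size is said to suffice for a correlation of 80% or more "between change in proliferation marker and expression of beta adrenergic receptors", with a confidence interval 30% wide.

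Neither place names a model, a type of coefficient or a covariate, or says whether change is absolute or relative.

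On tissue, the ADRB Receptor Analysis paragraph states: "Tumor samples from the initial biopsy and surgical resection will be deidentified and stained via IHC for these specific ADRB receptors". Section 6 also has biomarkers assessed on the biopsy. The tissue microarray in Section 4 is built from post-treatment blocks only ("30 cases, post-treatment"). No sentence links either time point to the correlation.

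On purpose, Sections 3 and 4 give among the reasons for the design "validating markers that may predict subsets of patients who will benefit from this drug", and the targeting of selected patients in later trials.

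**The concern.** There are two gaps, and they do not carry equal weight.

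**Which ADRB score.** A marker used to choose patients must be known before treatment. Section 4 itself expects tumors to change under beta blockade, since it plans to look for compensatory resistance. A score from the resected tumor may therefore be partly a consequence of the drug. If that score enters the correlation, the result cannot serve the stated purpose. This gap needs no numerical assumption.

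**What the correlation with change measures.** Baseline Ki-67 is one of the two terms in the change. If ADRB is associated with measured baseline Ki-67, part of its correlation with change may come from how proliferative the tumor looked at the start. If ADRB rises with baseline Ki-67, the artefact makes high-ADRB tumors appear to fall more, which is the result hoped for. A receptor could then be carried into a later trial as predictive when it only marks high starting values.

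**Working it through.** **1. The plan's own figure.** Fisher z interval for r = 0.80: atanh(0.80) = 1.099, SE = 1/sqrt(n - 3).

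- n = 30: 1.099 ± 1.96/sqrt(27) gives 0.618 to 0.901, width 0.283.
- n = 24 (30 less 20% dropout): 0.586 to 0.910, width 0.324.

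The stated width of 0.30 is met from 28 evaluable patients upward, so it reproduces for all 30 enrolled.

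**2. Inputs for the baseline question.** From the documents: 24 evaluable patients (30 x 0.8). Assumed, because the documents give no value: the correlation r between biopsy ADRB and measured baseline Ki-67 (0.3 to 0.6), and the correlation rho between pre and post Ki-67 (0.2 to 0.7). Also assumed: equal pre and post SDs, change as a simple difference (post minus pre), and no true link between ADRB and response.

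**3. General formula.** Let r_post be the correlation of biopsy ADRB with post-treatment Ki-67. Then

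corr(change, ADRB) = (r_post - r) / sqrt(2(1 - rho)).

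The documents do not fix r_post. Two readings of no link to response give different answers.

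- **Model A:** post Ki-67 is unrelated to ADRB once *measured* baseline is known. Then r_post = r x rho, and the formula becomes -r x sqrt((1 - rho)/2). The partial correlation given baseline is zero.
- **Model B:** pre and post are noisy readings of one true Ki-67, and ADRB tracks only the true value. Then r_post = r and the correlation with change is zero. The partial correlation given baseline is r(1 - rho)/sqrt((1 - r²)(1 - rho²)), which is not zero.

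**4. Numbers** (n = 24, 20,000 simulated trials per setting; the percentages are the share reaching p < 0.05 two-sided).

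| r | rho | Model A: change correlation by formula | A: change | A: adjusted | Model B: partial correlation by formula | B: change | B: adjusted |
|---|---|---|---|---|---|---|---|
| 0.3 | 0.7 | -0.12 | 8.5% | 5.0% | +0.13 | 5.2% | 9.2% |
| 0.4 | 0.5 | -0.20 | 16% | 5.1% | +0.25 | 4.6% | 22% |
| 0.6 | 0.5 | -0.30 | 30% | 4.9% | +0.43 | 5.2% | 56% |
| 0.6 | 0.2 | -0.38 | 46% | 4.9% | not possible | - | - |

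In the last row the simulated mean under model A is -0.37. Model B cannot produce that row, because it needs r no larger than sqrt(rho), and sqrt(0.2) = 0.45.

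Under A the change correlation misleads and the adjusted one does not. Under B it is the reverse. In neither model do the two expected values agree, so requiring agreement guards against both artefacts.

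**5. If the post-treatment score is used instead.** Suppose it merely tracks post-treatment Ki-67 with correlation g. By symmetry the induced correlation is +g x sqrt((1 - rho)/2), so the sign flips. At n = 25, rho = 0.5 and g = 0.3, 0.5 and 0.7, the change correlation is falsely significant in 11%, 23% and 41% of trials. Adjusting for baseline Ki-67 raises this to 24%, 62% and 95%. Adjustment is therefore no substitute for fixing the time point.

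**The case against.** The strongest objection is that correlation with change and baseline adjustment answer different questions when the predictor is not randomized (Lord's paradox), and neither is right in general. Under model B the planned analysis is sound and adjustment creates the error. This stands. A reader might infer that any ADRB-baseline association must produce a spurious correlation, or that adjusting always restores 5%. Both hold under model A only.

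Measurement noise is plausible here. Section 4 compares a biopsy with a surgical specimen, stained in different laboratories, with 400 cells counted by hand. Counting error alone is at most sqrt(0.25/400) = 2.5 percentage points, small beside the SD of 15% in Section 9. Most of the noise would have to come from area choice, specimen type or laboratory, which the documents do not quantify. Neither model can be ruled out.

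Three further objections also stand.

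- The documents give neither r nor rho. With r = 0 there is no artefact under either model.
- Section 9 sets no significance test for Aim 2. It sets a target correlation and an interval width, so the error rates above only gauge the size of the problem.
- The plan is silent on method; it has not committed to an unadjusted absolute change.

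A reader might also take the post-treatment microarray to mean that no pre-treatment predictor will exist. The documents do not support that, since biopsy staining is planned. What is missing is the statement that the biopsy score is the one used.

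**Conclusion.** The time-point gap holds on the text alone: both scores will exist, the aim needs the earlier one, and no sentence selects it.

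The baseline concern holds conditionally. If ADRB follows measured baseline Ki-67 as in model A, with r from 0.3 to 0.6 and rho from 0.2 to 0.7, the induced correlation is about -0.12 to -0.37. If ADRB follows only the true Ki-67 and the scatter is noise, it is zero. A reader might infer that the plan could produce a false correlation of 0.80. It could not by this route: even if ADRB equalled baseline Ki-67, the formula gives only -0.59 at rho = 0.3. The risk is a moderate correlation reported as predictive.

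The documents therefore support adding an adjusted analysis, not replacing the planned one. This is a modest but worthwhile correction to a secondary aim of a 30-patient pilot, because the result is meant to steer later trials.

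**What to change.** In Section 9:

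1. Name the biopsy ADRB score as the predictor, separately for ADRB1, ADRB2 and ADRB3.
2. Label post-treatment ADRB, and its change, as descriptive.
3. Keep the correlation with Ki-67 change. Beside it, as a prespecified sensitivity analysis and not a replacement, report the partial correlation with 95% CI from a regression of post-treatment Ki-67 on baseline Ki-67 plus biopsy ADRB.
4. State that a receptor will be called a candidate predictor only if the two analyses agree in direction and rough size.

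The cost is wording and a little more analysis, since all the data are already planned. The adjusted model spends one degree of freedom: at r = 0.80 the interval width goes from 0.283 to 0.289 with 30 patients (SE = 1/sqrt(26) in place of 1/sqrt(27)), and from 0.324 to 0.333 with 24. The conclusion will also be more cautious, and a real association may go unclaimed if the two analyses differ.
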